10.4 STATISTICAL APPENDICES

A Bayesian logistic regression model with overdose control will be used to guide dose escalation in this part of the trial. The BLRM is introduced in section [7.1](#), which also specifies the prior for the model. After patients in each cohort have completed at least one cycle of treatment, the prior distribution will be updated through Gibbs sampling procedures with the accumulated DLT data from the MTD evaluation period. Posterior probabilities for the rate of DLTs will be summarised from BLRM. Selection of the next dose will be based on these probabilities as well as on other safety and laboratory data.

The purpose of this statistical appendix is to present performance metrics (operating characteristics) that illustrate the precision of the design in estimating the MTD under various dose-toxicity relationships through computer simulation. These results are summarized in Table [10.4.1: 3](#) and Table [10.4.2: 3](#) for Part A and Part B respectively. In addition, recommendations of the next dose level by the BLRM with overdose control principle are also provided under various hypothetical outcome scenarios in early cohorts to show how it facilitates on-trial dose-escalation decisions (see Table [10.4.1: 1](#) for Part A and Table [10.4.2: 1](#) for Part B). For simplicity reasons, a cohort size of 3 patients who are all evaluable is assumed.

10.4.1 Part A

Hypothetical data scenarios:

Hypothetical data scenarios are shown in Table [10.4.1: 1](#). These scenarios reflect potential on-study data constellations and related escalation as allowed by the model and the 100% escalation limit. It is assumed that each cohort has exactly three patients who are all evaluable. For each scenario, the probability of overdose for the current dose, as well as the next potential dose and related probabilities of under-dosing, target dose, and over-dosing are shown.

For example, scenario 1 represents the case that no DLT is observed in the first three patients at the starting dose of 100 mg. In this case, the next optimal dose, i.e. the dose with the highest probability of being in the target interval, is 400 mg. Since the escalation is restricted to a maximum of 100 % from the previous dose per protocol, the next dose to be tested in the trial would be 200 mg. Similarly, scenario 4 represents the case that 3 patients have been treated at 100 mg and 3 at 200 mg, none of them with a DLT. In this case, the model requires to escalate to 400 mg.

Scenario 3 shows the case that 2 DLTs are observed in the first three patients at the starting dose of 100 mg. The model then allows the next dose to be de-escalated to 50 mg.

Finally, scenario 8, 9 and 10 illustrate a case where escalation has proceeded up to the highest dose of 400 mg, where the MTD could be declared at 400 mg.

Table 10.4.1: 1 Hypothetical data scenarios

Scenario	Dose (q.d. mg)	# Patients	# DLT	Current Dose: P (OD)	Next recommended dose	Next dose:		
						P (UD)	P (TD)	P (OD)
1	100	3	0	0.001	400*[200]	0.834	0.106	0.060
2	100	3	1	0.041	400*[200]	0.564	0.253	0.184
3	100	3	2	0.316	50	0.533	0.262	0.205
4	100	3	0					
	200	3	0	0.002	400	0.871	0.091	0.039
5	100	3	0					
	200	3	1	0.030	400	0.596	0.237	0.167
6	100	3	0					
	200	3	2	0.193	200	0.479	0.327	0.193
7	100	3	1					
	200	3	1	0.140	200	0.520	0.340	0.140
8	100	3	0					
	200	3	0					
	400	6	0	0.001	400	0.970	0.029	0.001
9	100	3	0					
	200	3	0					
	400	6	1	0.023	400	0.814	0.163	0.023
10	100	3	0					
	200	3	0					
	400	6	2	0.134	400	0.496	0.371	0.134
11	100	3	0					
	200	3	0					
	400	6	3	0.413	200	0.824	0.164	0.013
12	100	3	0					
	200	3	0					
	400	6	4	0.745	200	0.763	0.198	0.039

Operating characteristics:

Operating characteristics are a way to assess the long-run behaviour of a model by illustrating the precision of the design in estimating the MTD. Under an assumed true dose-toxicity curve,

Proprietary confidential information © 2021 Boehringer Ingelheim International GmbH or one or more of its affiliated companies

metrics such as the probability of recommending a dose with true DLT rate in the target interval can be approximated via simulation. Table [10.4.1: 2](#) describes 6 assumed true dose-toxicity scenarios which were used to assess the operating characteristics of the model. These scenarios reflect a wide range of possible cases as follows:

- Scenario 1: aligned with prior means
- Scenario 2: high-toxicity scenario
- Scenario 3: low-toxicity scenario
- Scenario 4: non-logistic dose-toxicity scenario
- Scenario 5: low-toxicity followed by high-toxicity
- Scenario 6: super high-toxicity scenario

Table 10.4.1: 2 Assumed true dose-toxicity scenarios

Scenario		Dose (mg q.d.)					
		40*	50	100	200	400	600*
1: Prior	P(DLT)	NA	0.022	0.032	0.053	0.107	0.181
2: High Tox		NA	0.194	0.253	0.425	0.527	NA
3: Low Tox		NA	0.008	0.028	0.054	0.143	0.181
4: Non-Logistic		NA	0.032	0.098	0.268	0.467	NA
5: Low-High		NA	0.008	0.052	0.241	0.335	NA
6: Super High Tox		0.260	0.450	0.578	0.660	0.737	NA

* To allow the model to implement the above scenarios and to evaluate the operating characteristics, 40 mg and 600 mg doses were included even if they will not be tested in the trial.

For each of these scenarios, 1000 trials were simulated. Each cohort consisted of 3 patients and dose escalation complied with the following rules:

- Escalate to the dose which maximises the probability of the targeted toxicity region and satisfies the overdose criterion if it is $\leq 100\%$ increase from the current dose.
- If the recommended dose satisfying the overdose criterion is $> 100\%$ increase in dose, then escalate to the highest dose level which is $\leq 100\%$ increase from the current dose.

The MTD was considered reached if at least 6 patients have been evaluated at a dose level which is the model's recommendation for the next dose cohort and for which the posterior probability of targeted toxicity was at least 50%.

It was then assessed how often a dose was declared as MTD with true DLT rate in the under-, targeted or over-dose range.

Furthermore, the average, minimum and maximum number of patients per trial and the average number of DLTs per trial are reported. Results are shown in Table [10.4.1: 3](#).

Table 10.4.1: 3 Simulated operating characteristics

	% of trials declaring a MTD with true DLT rate in				# Patients	# DLTs
	underdose	target dose	overdose	Stopped	Mean (Min-Max)	Mean (Min-Max)
1	17.7	82.3	0	0	16.5 (12-42)	1.9 (1-7)
2	0	45.4	37.8	16.8	12.9 (3-30)	4.5 (1-11)
3	22.2	77.6	0	0.2	16.4 (12-42)	1.9 (0-6)
4	18.8	52.8	27.1	1.3	13.7 (6-33)	3.7 (1-9)
5	7.4	42.8	49.5	0.3	13.4 (6-27)	3.0 (1-8)
6	0	0.1	11.6	88.3	8.1 (3-27)	4.5 (2-12)

In Scenario 1, which reflects the case that the true dose-toxicity is aligned with prior means, 82.3% of the simulated trials declared a dose as MTD with true DLT rate under the targeted dose range.

Scenario 2 (high-toxicity scenario) shows, that when the true DLT rate is high, i.e. the majority dose levels with true DLT rate above the target interval, 45.4% of the simulated trials declared a dose as MTD with true DLT rate in the targeted dose range. 16.8% of the trials were stopped without declaring a MTD since all dose levels were too toxic. This is an expected situation for a high-toxicity scenario.

Scenario 3 shows that when the true DLT rate is low, 77.6% of the simulated trials declared a dose as MTD with true DLT rate in the target dose range.

Scenario 4 represents a case where the assumed true dose-toxicity curve does not follow a logistic shape. In this scenario, 52.8% of trials declared MTDs with true DLT rate in the target interval.

Scenario 5 shows that when the true DLT rate is low-high, 42.8% of the simulated trials declared a dose as MTD with true DLT rate in the targeted dose range. 428 trials declared 200 mg as the MTD, and 495 trials declared 400 mg as the MTD.

Scenario 6 shows that when the true DLT rate is super high, most of simulated trials stopped, since none of the doses is considered tolerable anymore. This is an expected situation for a super high-toxicity scenario.

The mean patient numbers range from 8.1 patients (Scenario 6) to 16.5 patients (Scenario 1) and the maximum number of patients was 42. Therefore, the patient numbers are as expected and increase when moving away from the high-toxicity scenario.

By reviewing the metrics presented in Table [10.4.1: 3](#), it can be seen that the model is not sensitive to different scenarios of truth. In general, this model is conservative due to the overdose control criteria. In most scenarios, the probabilities of recommending a dose with true $P(DLT) \geq 33\%$ as MTD are much smaller than probabilities of recommending a dose with true $P(DLT)$ between 16% and 33% as MTD.

On-study recommendations based on the model are consistent with the clinical decision making process, and should be considered in conjunction with other available clinical information by the BI clinical trial team and trial investigators in deciding the dose levels to be tested in order to determine the MTD estimate.

R version 3.5.1 and JAGS was used for data scenarios and simulations.

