4.1.3 Dose-finding scheme

The dose is planned to be tested in cohorts at pre-defined provisional dose levels. The provisional dose levels to be assigned to different cohorts of patients are listed in Tables [4.1.3: 1](#) and [4.1.3: 2](#). Intermediate or lower dose levels may be investigated if agreed in the SMC, depending on the number of DLTs observed in the trial. The highest planned dose of BI 891065 is 400 mg per day.

Table 4.1.3: 1 Example of dose escalation in Part A

Dose level	Proposed daily dose of BI 891065*	Participating countries
1	100 mg	Japan
2	200 mg **	Japan
3	400 mg **	Japan and Taiwan

*The total daily dose will be given in q.d. or b.i.d. dosing schedule.

**Actual dose level and dosing schedule for a cohort will be communicated separately as determined by the SMC. Intermediate or lower dose level(s) may be investigated depending on the latest DLT rate estimate.

Table 4.1.3: 2 Example of dose escalation in Part B

Dose level	Proposed daily dose of BI 891065*	Proposed dose of BI 754091 (every three weeks)	Participating countries
1	200 mg **	240 mg	Japan and Taiwan
2	400 mg **	240 mg	Japan and Taiwan

* The total daily dose will be given in q.d. or b.i.d. dosing schedule.

**Actual dose level and dosing schedule for a cohort will be communicated separately as determined by the SMC. Intermediate or lower dose level(s) may be investigated depending on the latest DLT rate estimate.

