7. STATISTICAL METHODS AND DETERMINATION OF SAMPLE SIZE

7.1 STATISTICAL DESIGN – MODEL

7.1.1 Part A

The trial will be performed as an open-label trial. The objective of the design is to determine the MTD defined as the highest dose with less than 25% risk of the true DLT rate being above 0.33 (EWOC criterion). The dose-finding of Part A will be guided by a Bayesian 2-parameter logistic regression model with overdose control ([R13-4806](#); [R13-4803](#)).

The model is given as follows:

$$\text{logit}(\pi_d) = \log(\alpha) + \beta * \log(d/d^*),$$

where $\text{logit}(\pi) = \log(\pi/(1-\pi))$.

π_d represents the probability of having a DLT in the MTD evaluation period at dose d , $d^* = 200$ mg is the reference dose, allowing for the interpretation of α as the odds of a DLT at dose d^* , and $\theta = (\log(\alpha), \log(\beta))$ with $\alpha, \beta > 0$ is the parameter vector of the model.

The estimated probability of a DLT at each dose level from the model will be summarized using the following intervals:

Under toxicity: [0.00, 0.16)

Targeted toxicity: [0.16, 0.33)

Over toxicity: [0.33, 1.00]

The BLRM-recommended dose for the next cohort is the level with the highest posterior probability of the DLT rate falling in the target interval [0.16, 0.33) among the doses fulfilling EWOC. Applying the EWOC criterion, it should be unlikely (<25% posterior probability) that the DLT rate at that dose will exceed 0.33. However, the maximum allowable dose increment for the subsequent cohort will be no more than 100 %.

The MTD may be considered reached if one of the following criteria is fulfilled:

- The posterior probability of the true DLT rate in the target interval [0.16 – 0.33] of the MTD is above 0.5, OR
- At least 12 patients have been treated in the dose escalation phase of the trial, of which at least 6 at the MTD.

The SMC may decide stopping the dose escalation phase after the criterion for MTD is fulfilled. Further patients may be included to confirm this MTD estimate. If no DLT is observed at a dose of which the efficacy is considered sufficient, the SMC may decide to include an additional number of patients at this dose level and to declare this dose as the dose recommended for further testing.

The BLRM is set up for a fixed dosing schedule of once daily (q.d.) across dose levels of BI 891065. For the purpose of dose-toxicity modelling, a b.i.d. regimen will be converted in

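### The 82.3% and 77.6% target-range results for Part A are all selections of a 600 mg dose outside the trial, and the conclusions and stopping rule printed with them do not match the table

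*Protocol*

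**What the plan says.** Section 4.1.3 fixes the range: "The highest planned dose of BI 891065 is 400 mg per day". Section 7.1.1 defines the target interval as [0.16, 0.33) and overdose as 0.33 or more. It lets the MTD be considered reached on either of two grounds. One is a posterior probability of the target interval greater than one half. The alternative reads: "At least 12 patients have been treated in the dose escalation phase of the trial, of which at least 6 at the MTD".

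Section 10.4.1 evaluates the design by simulation. The footnote to Table 10.4.1: 2 states that "40 mg and 600 mg doses were included even if they will not be tested in the trial". The simulated stopping rule is described differently from Section 7.1.1: at least six patients at the dose the model recommends next, and also a dose "for which the posterior probability of targeted toxicity was at least 50" per cent.

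On the results in Table 10.4.1: 3, the text says for Scenario 1 that "82.3% of the simulated trials declared a dose as MTD with true DLT rate under the targeted dose range" (the table puts this figure in the target column) and for Scenario 3 that "77.6% of the simulated trials declared a dose as MTD with true DLT rate in the target dose range". It concludes that "it can be seen that the model is not sensitive to different scenarios of truth" and that "this model is conservative due to the overdose control criteria", adding that overdose selections are far rarer than target selections in most scenarios.

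**The concern.** Section 7.6 makes no power calculation and refers to Section 10.4 for how a design with about 12 patients in Part A performs. A reader of the text under Table 10.4.1: 3 would take 82.3% and 77.6% as the chance of finding a target-range MTD when toxicity is as expected or low. If those trials all chose a dose that cannot be given, the figures do not describe this trial. If the concluding sentences and the printed stopping rule also disagree with the table, the reader cannot tell what was simulated or how often the design picks too toxic a dose.

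**Working it through.** **Step 1. Classify the assumed true rates.** The rates come from Table 10.4.1: 2, the interval from Section 7.1.1 and the outcome percentages from Table 10.4.1: 3.

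| Scenario | Doses in [0.16, 0.33) | Doses at 0.33 or more | Stated target % | Stated overdose % | Stopped % |
|---|---|---|---|---|---|
| 1 | 600 mg (0.181) | none | 82.3 | 0 | 0 |
| 2 | 50 mg (0.194), 100 mg (0.253) | 200 mg (0.425), 400 mg (0.527) | 45.4 | 37.8 | 16.8 |
| 3 | 600 mg (0.181) | none | 77.6 | 0 | 0.2 |
| 4 | 200 mg (0.268) | 400 mg (0.467) | 52.8 | 27.1 | 1.3 |
| 5 | 200 mg (0.241) | 400 mg (0.335) | 42.8 | 49.5 | 0.3 |
| 6 | 40 mg (0.260) | 50 to 400 mg (0.450 to 0.737) | 0.1 | 11.6 | 88.3 |

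In Scenarios 1 and 3 a target selection can only be 600 mg. In Scenario 6 it can only be 40 mg, which is also outside the trial. This needs no simulation.

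**Step 2. Overdose against target.** Scenarios 1 and 3 contain no overdose, so their 0% is automatic. For the others:

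- Scenario 2: 37.8 / 45.4 = 0.83
- Scenario 4: 27.1 / 52.8 = 0.51
- Scenario 5: 49.5 / 42.8 = 1.16
- Scenario 6: 11.6% overdose against 0.1% target, with 88.3% stopped

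Of the four scenarios where overdose is possible, it exceeds target in two and is at least half of target in the other two. Counting Scenarios 1, 3 and, generously, 4 as far smaller gives three of six. Target selection runs from 0.1% to 82.3% across the scenarios.

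**Step 3. Reproduce the model.** logit(π_d) = log α + β log(d/200), with the prior of Table 7.1.1: 2: weight 0.9 on means (-3.66, -0.28), SDs (1.20, 0.83), correlation -0.10; weight 0.1 on means (-3, 0), SDs (2, 1), correlation 0. Grid integration gives 0.811/0.115/0.074 (under/target/over) at 400 mg, against 0.813/0.115/0.072 in Table 7.1.1: 3. All 12 rows of Table 10.4.1: 1 are matched to about 0.01.

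**Step 4. Reproduce the stated percentages.** Settings: cohorts of 3, start at 100 mg, overdose probability below 25%, at most a 100% increase, Section 7.1.1 stopping rule, 600 mg allowed, 5,000 trials.

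| Scenario | Source | Under/target/over % | Mean N | Max N |
|---|---|---|---|---|
| 1 | Re-simulated | 18.4 / 81.6 / 0 | 15.3 | 24 |
| 1 | Stated | 17.7 / 82.3 / 0 | 16.5 | 42 |
| 3 | Re-simulated | 22.7 / 77.3 / 0 | 15.2 | 24 |
| 3 | Stated | 22.2 / 77.6 / 0 | 16.4 | 42 |

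Every re-simulated target selection is at 600 mg. The same rule also comes close in Scenarios 2, 4 and 5 (1,000 trials each): target/overdose 45.4/36.6, 53.4/27.7 and 42.0/49.9.

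**Step 5. Restrict to the trial's doses.** Same rule, 50 to 400 mg, 5,000 trials: 0% target in both scenarios, with 95.6% (Scenario 1) and 92.1% (Scenario 3) of trials ending at 400 mg and a mean of 12.1 patients. Adding 300 mg (the modelled equivalent of 200 mg b.i.d.) at assumed true rates of 0.08 and 0.10 still gives 0% target, with 98.1% and 96.3% at 400 mg.

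**Step 6. Test the printed simulation rule.** Three checks:

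- *Against the hypothetical data.* Section 10.4.1 says an MTD could be declared at 400 mg in hypothetical data scenarios 8, 9 and 10. Table 10.4.1: 1 gives target probabilities there of 0.029, 0.163 and 0.371, all below 0.50.
- *Against zero-DLT trials.* Table 10.4.1: 3 shows a minimum of 0 DLTs in Scenario 3, yet 22.2 + 77.6 + 0 + 0.2 = 100, so every trial declared an MTD or stopped. With no DLT, the target probability at 600 mg is 0.147 a priori, 0.122 after 0/3 at 100 and 200 mg, and 0.057 after 0/3 at each of 100, 200, 400 and 600 mg. Such a trial cannot reach 0.50, nor can it stop for toxicity.
- *By simulation.* With 600 mg allowed and an assumed cap of 42 patients (1,000 trials), the printed rule leaves 45.5% (Scenario 1) and 41.7% (Scenario 3) unresolved, with mean N of 33.5 and 32.9 against the stated 16.5 and 16.4. With an assumed cap of 60, 31.7% and 35.4% remain unresolved, with mean N of 39.8 and 40.7.

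**The case against.** The added doses are disclosed in the footnote and the 600 mg rate is printed, so nothing is hidden and no percentage is miscalculated. A 0% target share on trial doses is not a design failure: Section 3.1 allows escalation to end once safety at the highest planned dose is confirmed without an MTD, and Section 2.1.1 lets the SMC name a recommended dose independently of the MTD. Ending at 400 mg in Scenarios 1 and 3 is the intended outcome. The printed rule describes only the simulation, and the selection percentages already track Section 7.1.1. In Scenario 5, 400 mg is only 0.005 above the limit, and in Scenario 6 the 88.3% stopped shows overdose control working. By protocol version 5 the primary and secondary endpoint assessments were complete, and the SAP records that Part B was cancelled.

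Much of this stands and limits the size of the point: the on-study rule is not in doubt, and no dosing decision or final analysis uses the table. It does not rescue the text. The results paragraphs quote both percentages without the caveat and give no result on the trial's doses. By contrast, the Part B text in Section 10.4.2 names the selected combination in its Scenarios 1 and 3. Setting Scenario 5 aside, the claim about most scenarios still fails. The stopping-rule sentence is wrong on the protocol's own figures.

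**Conclusion.** The concern holds. The 82.3% and 77.6% describe selection of a dose above the planned maximum. On the trial's doses the target share in those scenarios is 0%, a property of the assumed rates rather than a wrong choice of dose. The target figures that do describe the trial are 45.4%, 52.8% and 42.8%, with 37.8%, 27.1% and 49.5% overdose in the same scenarios. The conclusions on sensitivity and on the rarity of overdose selection are not supported, and conservatism cannot be read from scenarios in which overdose was impossible.

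The printed stopping rule is not the one simulated. The Section 7.1.1 rule fits the selection percentages far better but does not explain the maximum of 42 patients (24 in the re-simulation), and its Scenario 6 results are less close (17.0% overdose and 82.3% stopped in 1,000 trials). The rule actually run therefore remains undocumented.

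The first two findings follow from the printed tables alone. The size of the stopping-rule discrepancy rests on re-simulation with assumed caps of 42 or 60, but the conflicts with Table 10.4.1: 1 and with the zero-DLT minimum need no cap. The harm is confined to the stated performance of the design.

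**What to change.** - Re-run Table 10.4.1: 3 on the doses the trial can give (up to 400 mg) under the Section 7.1.1 rule, reporting selection by dose and stating the rule and any patient cap.
- For Scenarios 1 and 3, report the share of trials ending at the highest planned dose with a true rate below target. Failing that, label 82.3% and 77.6% as 600 mg selections outside the trial's range. Label the Scenario 6 target figure as 40 mg in the same way.
- Replace the sentences on insensitivity, conservatism and the rarity of overdose selection with the overdose and target figures for the scenarios where overdose is possible.
- Reconcile the simulated stopping rule with Section 7.1.1 and with the text on hypothetical data scenarios 8 to 10.

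The cost is a few hours of simulation and some appendix wording. The stated figures become less favourable. No extra patients are needed, and neither the on-study model nor the final analysis changes. Nothing here bears on which doses should be tested.

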10.4.2 Part B

Hypothetical data scenarios:

Hypothetical data scenarios are shown in Table [10.4.2: 1](#). These scenarios reflect potential on-study data constellations and related escalation as allowed by the model and the 100% escalation limit. It is assumed that each cohort has exactly three patients who are all evaluable. For each scenario, the probability of overdose for the current dose, as well as the next potential dose and related probabilities of under-dosing, target dose, and over-dosing are shown.

For example, scenario 1 represents the case that no DLT is observed in the first three patients at the starting dose combination of 200 / 240. In this case, the next optimal dose combination is 400 / 240.

Scenario 2 shows the case that one patient out of the 3 treated patients at 200 / 240 experiences a DLT, then the model would still recommend to treat the next patient with the same dose combination of 200 / 240.

Scenario 3 shows the case that 2 DLTs are observed in the first three patients at the starting dose combination of 200 / 240. The model then allows the next dose combination to be de-escalated to 100 / 240.

Finally, scenario 4, 5 and 9 illustrate a case where escalation has proceeded up to the highest dose combination of 400 / 240, where the MTD could be declared at that dose combination.

Table 10.4.2: 1 Hypothetical data scenarios

Scenario	Dose combination (mg)	# Patients	# DLT	Current Dose: P (OD)	Next recommended dose combination	Next dose:		
						P (UD)	P (TD)	P (OD)
1	200 / 240	3	0	0.024	400 / 240	0.572	0.251	0.178
2	200 / 240	3	1	0.110	200 / 240	0.501	0.389	0.110
3	200 / 240	3	2	0.350	100 / 240	0.485	0.369	0.147
4	200 / 240	3	0					
	400 / 240	6	0	0.015	400 / 240	0.857	0.128	0.015
5	200 / 240	3	0					
	400 / 240	6	1	0.085	400 / 240	0.567	0.348	0.085
6	200 / 240	3	0					
	400 / 240	6	2	0.282	200 / 240	0.632	0.350	0.018
7	200 / 240	3	0					
	400 / 240	6	3	0.567	200 / 240	0.420	0.523	0.057
8	200 / 240	3	0					
	400 / 240	6	4	0.813	200 / 240	0.268	0.594	0.138
9	200 / 240	3	1					
	400 / 240	6	1	0.173	400 / 240	0.392	0.436	0.173
10	200 / 240	3	1					
	400 / 240	6	2	0.422	200 / 240	0.406	0.526	0.068

Operating characteristics:

Operating characteristics are a way to assess the long-run behaviour of a model by illustrating the precision of the design in estimating the MTD. Under an assumed true dose-toxicity curve, metrics such as the probability of recommending a dose with true DLT rate in the target interval can be approximated via simulation. Table [10.4.2: 2](#) describes 6 assumed true dose-toxicity scenarios which were used to assess the operating characteristics of the model. These scenarios reflect a wide range of possible cases as follows:

- Scenario 1: aligned with prior means
- Scenario 2: high-toxicity scenario
- Scenario 3: low-toxicity scenario
- Scenario 4: non-logistic dose-toxicity scenario
- Scenario 5: low-toxicity followed by high-toxicity
- Scenario 6: super high-toxicity scenario

Table 10.4.2: 2 Assumed true dose-toxicity scenarios

Scenario		Dose combination (mg)				
		25 / 240	50 / 240	100 / 240	200 / 240	400 / 240
1: Prior	P(DLT)	0.081	0.093	0.114	0.159	0.257
2: High Tox		0.161	0.194	0.253	0.398	0.607
3: Low Tox		0.068	0.095	0.101	0.124	0.251
4: Non-Logistic		0.023	0.032	0.150	0.168	0.467
5: Low-High		0.011	0.028	0.072	0.170	0.535
6: Super High Tox		0.260	0.450	0.578	0.660	0.737

For each of these scenarios, 1000 trials were simulated. Each cohort consisted of 3 patients and dose escalation complied with the following rules:

- Escalate to the dose combination which maximises the probability of the targeted toxicity region and satisfies the overdose criterion if it is $\leq 100\%$ increase from the current dose.
- If the recommended dose combination satisfying the overdose criterion is $> 100\%$ increase in dose, then escalate to the highest dose level which is $\leq 100\%$ increase from the current dose.

The MTD was considered reached if at least 6 patients have been evaluated at a dose level which is the model's recommendation for the next dose cohort and for which the posterior probability of targeted toxicity was at least 50%.

It was then assessed how often a dose combination was declared as MTD with true DLT rate in the under-, targeted or over-dose range.

Furthermore, the average, minimum and maximum number of patients per trial and the average number of DLTs per trial are reported. Results are shown in Table [10.4.2: 3](#).

Table 10.4.2: 3 Simulated operating characteristics

	% of trials declaring a MTD with true DLT rate in				# Patients	# DLTs
	underdose	target dose	overdose	Stopped	Mean (Min-Max)	Mean (Min-Max)
1	55.1	43.6	0.0	1.3	11.5 (3-42)	2.2 (0-7)
2	0.0	29.8	48.5	21.7	10.3 (3-30)	3.9 (1-11)
3	47.7	51.5	0.0	0.8	11.8 (3-42)	2.1 (0-6)
4	3.9	79.6	14.7	1.8	11.1 (3-30)	2.9 (1-8)
5	2.7	88.6	7.7	1	11.1 (3-24)	3.0 (1-7)
6	0	7.8	27.6	64.6	11.0 (3-30)	5.2 (2-13)

In Scenario 1, which reflects the case that the true dose-toxicity is aligned with prior means, 43.6% of the simulated trials declared the dose combination 400 / 240 as MTD with true DLT rate under the targeted dose range.

Scenario 2 (high-toxicity scenario) shows, that when the true DLT rate is high, i.e. the majority dose levels with true DLT rate above the target interval, only 29.8% of the simulated trials declared a dose combination as MTD with true DLT rate in the targeted dose range, and 48.5% in the overdose interval. 21.7% of the trials were stopped without declaring a MTD since all dose levels were too toxic. This is an expected situation for a high-toxicity scenario.

Scenario 3 shows that when the true DLT rate is low, 51.5% of the simulated trials declared the dose combination 400 / 240 mg as MTD with true DLT rate under the targeted dose range, and 47.7% of the simulated trials declared a MTD in the underdose interval.

Scenario 4 represents a case where the assumed true dose-toxicity curve does not follow a logistic shape. In this scenario, 79.6% of trials declared MTDs with true DLT rate in the target interval, and only a few trials declared MTDs with true DLT rate in the underdose interval. This illustrates that the model is not sensitive to model misspecification.

Scenario 5 shows that when the true DLT rate is low-high, 88.6% of the simulated trials declared a dose as MTD with true DLT rate in the targeted dose range.

Scenario 6 shows that when the true DLT rate is super high, 64.6% of simulated trials stopped, since none of the doses is considered tolerable anymore. This is an expected situation for a super high-toxicity scenario.

The mean patient numbers range from 10.3 patients (Scenario 2) to 11.8 patients (Scenario 3) and the maximum number of patients was 42. Therefore, the patient numbers are as expected and increase when moving away from the high-toxicity scenario.

In summary, the considered data scenarios show a reasonable behaviour of the model and the operating characteristics demonstrate a good precision of MTD determination.

On-study recommendations based on the model are consistent with the clinical decision making process, and should be considered in conjunction with other available clinical information by the BI clinical trial team and trial investigators in deciding the dose levels to be tested in order to determine the MTD estimate.

R version 3.5.1 and JAGS was used for data scenarios and simulations.

